In the literature there is very little observational data for the changes in peripheral limb skin temperature following regional anaesthesia in the obstetric population. It has been documented previously in the non-pregnant population that the blockade of sympathetic nerve fibres by regional anaesthesia (including spinal, epidural and lumbar plexus anaesthesia) results in vasodilation of peripheral blood vessels and an increase in the blood flow to the skin, increasing the peripheral skin temperature¹⁻⁷. Saito et al reviewed the thermoregulatory effects of spinal and epidural anaesthesia during caesarean delivery but did not review the changes in peripheral limb skin temperature⁸. Griffin and Reynolds explored the correlation between sensory block asymmetry and a disparity in foot temperature following epidural bupivacaine administration in labour. Their findings indicated a clear association between sensory block asymmetry and the difference between the temperature of the feet. This difference can be detected simply by feeling the feet⁹. However, they did not review findings following spinal anaesthesia. The hypothesis of this study is that peripheral skin temperature will increase following regional anaesthesia/analgesia due to sympathetic block and that this temperature change could potentially be used as an indicator of potential efficacy of regional anaesthesia/analgesia. Spinal anaesthesia should reliably produce a bilateral sympathetic block. Therefore if a sympathetic block produces an increase in peripheral temperature this effect should be observable in women who have successful spinal anaesthesia for caesarean section. We propose measuring this peripheral foot temperature with Covidien Mon-a-Therm skin temperature probes and a Braun Welch Allyn tympanic membrane thermometer device. If this effect is found then this finding could be investigated in future studies to determine the value of using peripheral temperature measurement with a Braun Welch Allyn tympanic membrane thermometer device, as a marker and predictor of the efficacy of labour epidural analgesia.

Primary research question:

The hypothesis is that peripheral skin temperature of the dorsum of the feet will rise bilaterally following establishment of a spinal anaesthetic block and that the peripheral skin temperature will change with regression of the spinal anaesthetic block.

Secondary research question:

The secondary hypothesis is that an infrared tympanic thermometer could be as reliable a method of measuring temperature as a skin temperature probe and therefore be a practical accessible method for measuring peripheral skin temperature in delivery rooms.

Methods:

This is an observational study. We will obtain ethics committee approval for conducting the study. ASA 1 and 2 full term (37-42 weeks), parturients with singleton pregnancy, normal placental position, scheduled for category 4 LSCS under 'single-shot' spinal anaesthesia will be recruited. We intend to recruit 60 parturients. The parturients will undergo an informed consent process including an explanation of the methods and risks of the study. A patient information leaflet will be provided for the parturients.

The data will be collected on a password protected spread-sheet with no patient identifiable information. A grant for funding will be applied for from the Obstetric Anaesthetists' Association.

Prior to establishment of spinal anaesthesia, the skin temperature of the women's feet will be measured on the dorsum of the right and left feet above space between the 2nd and 3rd metatarsal bones while she is lying supine with left lateral tilt. The temperature will be measured by Covidien Mon-a-Therm skin temperature probes and a Braun Welch Allyn tympanic membrane thermometer device. Following spinal injection when the woman is lying supine with lateral tilt, the temperature will be re-measured by Covidien Mon-a-Therm skin temperature probes and a Braun Welch Allyn tympanic membrane thermometer device. The skin temperature of the women's feet will be monitored continuously by the Covidien Mon-a-Therm skin temperature probes using the GE Healthcare monitor with readings transcribed every 1 minute by the research investigator until transfer onto the bed at the end of surgery. The skin temperature of the women's feet will be measured and recorded every 1 minute using a Braun Welch Allyn tympanic membrane thermometer device until the sterile drapes are applied prior to commencing the operation and then again after removal of the drapes prior to transfer onto the bed. Following transfer to the post-operative recovery area, the skin temperature of the women's feet will be measured and recorded every 10 minutes using a Braun Welch Allyn tympanic membrane thermometer device until discharged to the ward from the recovery area (usually 2 hours from departmental guidelines).

Theatre room temperature will be measured and recorded at the start of anaesthesia and at the end of surgery using a room thermometer. Surgical drapes will be applied over the parturient's lower limbs during the caesarean section procedure as per our routine practice. The ambient temperature under the surgical drapes will be measured and recorded at the start of anaesthesia and at the end of surgery using a room thermometer.

Tympanic temperature will be measured by a Braun Welch Allyn tympanic membrane thermometer device before spinal anaesthesia and then every 30 minutes until the end of surgery as per NICE clinical guideline 65.

Spinal anaesthesia will be conducted as per usual practice. All intravenous fluids will be given through a fluid warmer.

Patient data to be recorded will include: Age, Weight, Height, BMI, total dose of intra-operative vasopressor given, highest estimated dermatome level of anaesthesia to cold (ethyl chloride spray) bilaterally prior to commencing surgery, level motor block using straight leg raise as per normal

practice when anaesthesia ready for surgery, duration of surgery, estimated blood loss, total volume of intravenous fluids given (including any blood products).

Dermatome level of anaesthesia will be measured to cold (ethyl chloride spray) level and motor block will be measured using straight leg raise as per normal practice, in recovery, every 30 minutes.

6 parturients will be recruited as a control group. The skin temperature of these women's feet will be measured on the dorsum of the right and left feet above space between the 2nd and 3rd metatarsal bones while she is lying supine with left lateral tilt in theatre. The temperature will be measured by Covidien Mon-a-Therm skin temperature probes and a Braun Welch Allyn tympanic membrane thermometer device. The sterile drapes will be applied and the skin temperature of the women's feet will be monitored continuously by the Covidien Mon-a-Therm skin temperature probes using the GE Healthcare monitor with readings transcribed every 1 minute by the research investigator for 30 minutes. After 30 minutes, the skin temperature of the women's feet will be measured and recorded every 1 minute using a Braun Welch Allyn tympanic membrane thermometer device for 5 minutes. Theatre room temperature will be measured and recorded for this control group of parturients. The ambient temperature under the surgical drapes will be measured and recorded using a room thermometer.

Inclusions / exclusions:

Parturients will be excluded from the study if they refuse or if they have medical conditions that may affect their peripheral temperature and therefore the results of the study. Our exclusion criteria are: Parturients converted to other forms of anaesthesia (not just spinal anaesthesia); Parturients with a pyrexia / sepsis; Parturients with peripheral vascular disease (including Raynaud's); Parturients with cardiovascular disease; Parturients with diabetes mellitus (gestational, type 1 or 2); Hypertensive disorders of pregnancy; ASA 3+ Parturients; BMI >40 or <18; Parturient refusal.

Consent:

We will assess the participants to check that they have capacity and therefore we will obtain valid consent from them. We will confirm that participants understand the purpose and nature of the research; understand what the research involves, the benefits (or lack of benefits), risks and burdens; understand the alternatives to taking part. We will also confirm that participants are able to retain the information long enough to make an effective decision, are able to make a free choice and are capable of making this particular decision at the time it needs to be made.

Informed consent will be taken from participants themselves by anaesthetists who have completed good clinical practice. Informed consent will be taken on a written consent form after a patient information leaflet detailing the study has been provided and a discussion of the details of the study has taken place.

Risks, burdens and benefits:

We have chosen methods for measuring skin temperature that are safe for patient use and already easily available in our hospital. Therefore these methods could be readily used if the results of the

trial mean that this method of temperature measurement to assess regional block can be extended to routine clinical practice.

The main risk may be allergy or skin reaction to the adhesive used on the skin temperature probe. However the probes are used routinely already in the hospital to measure skin temperature and therefore the risk is low.

Confidentiality:

Person-identifiable information will not be used unless it is absolutely necessary. If person-identifiable information is used, the minimum necessary will be used. Access to person-identifiable information will be on a strict need-to-know basis. Everyone with access to person-identifiable information will be made aware of their responsibilities. The data will be collected on a password protected spread-sheet with no patient identifiable information. If any problems arise from the processing of identifiable data these will be handled in line with data protection laws.

At the end of the study personal data will be kept for 6-12 months in case we need to check it, but anonymised research data will be kept for 10 years. This data will be saved for the purposes of data verification in a separate key, on password protected Cambridge University Hospitals NHS Foundation Trust secure computers linked to the study data by a unique participant ID.

Regulatory approval:

Before the start of the study, the following approvals will be sought:

- Health Research Authority (HRA) Approval
- NHS Research Ethics Committee (REC) review
- Confirmation of Capacity and Capability from the NHS research site.

An annual progress report (APR) will be submitted to the NHS REC within 30 days of the anniversary date on which the favourable opinion was given, and annually until the study is declared ended. It is the responsibility of the study team to produce the annual reports as required.

The study team will notify the NHS REC of the end of the study. If the study is ended prematurely, the study team will notify the NHS REC, including the reasons for the premature termination

Within one year after the end of the study, the study team will submit a final report with the results, including any publications/abstracts, to the NHS REC.

Peer review:

The study has received independent peer review from the CUH Research Advisory Committee.

Indemnity:

NHS indemnity will apply for the design, management and conduct of the study.

Amendments:

All amendments to the protocol will be discussed with the CUHNFT R&D department and submitted for HRA and REC review. Amendments submitted for regulatory review will not be implemented until the necessary regulatory approvals are received.

References:

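### In the 6 controls, probe transcription is scheduled to stop before the 5-minute infrared series, leaving 48 to 60 infrared readings without a same-minute probe reading (minor, cheap to mend)

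*Protocol*

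**What the plan says.** All of this is in the Methods section of the Protocol.

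**Controls.** The group is small: "6 parturients will be recruited as a control group". Both devices are used on each foot at baseline. Then "The sterile drapes will be applied and the skin temperature of the women's feet will be monitored continuously" by the skin probes, with "readings transcribed every 1 minute by the research investigator for 30 minutes". The infrared series follows: "After 30 minutes, the skin temperature of the women's feet will be measured and recorded every 1 minute using a Braun Welch Allyn" thermometer, for 5 minutes. No probe transcription is scheduled in those 5 minutes. The text limits the transcription to 30 minutes; it does not say that the probe comes off.

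**Spinal cohort.** The target is stated as "We intend to recruit 60 parturients". Both devices are used before the block: "Prior to establishment of spinal anaesthesia, the skin temperature of the women's feet will be measured on the dorsum" of each foot. Probe values are then transcribed every minute up to transfer onto the bed. Infrared readings are taken every minute "until the sterile drapes are applied prior to commencing the operation" and "then again after removal of the drapes prior to transfer onto the bed".

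**Aim served.** The secondary research question is whether the infrared thermometer is as reliable as the skin probe for measuring foot temperature.

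**The concern.** A comparison of two thermometers on a foot whose temperature may be changing needs readings taken at the same time. The spinal cohort schedule provides this in theatre: every infrared reading there falls while the probe is still being transcribed. The control schedule does not, and the protocol gives no reason for the difference. On the plain reading, the latest scheduled probe value is 1 to 5 minutes old when each control infrared reading is taken.

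At stake is one particular kind of pair. After draping, the spinal cohort's infrared readings come from women with a block. The controls are the only women without a spinal who have infrared readings after draping. A probe value that was never written down cannot be recovered at the analysis stage, so the schedule is the place to settle this.

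**Working it through.** The protocol gives no count of paired readings and no sample-size derivation, so there is no stated figure to reproduce. The check is a direct count.

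**Inputs (Protocol, Methods):** 6 control women; 2 feet each; probe every minute for 30 minutes; infrared every minute for 5 minutes, after the 30 minutes; spinal cohort of 60.

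**Assumption:** one infrared reading per foot per minute.

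**Step 1: unpaired control infrared readings.** The formula is women x feet x infrared minutes with no scheduled probe value. The result depends on how minute 30 is treated, which the text leaves open.

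| Infrared minutes | Last probe minute | Infrared readings | Paired | Unpaired |
|---|---|---|---|---|
| 31 to 35 (plain reading) | 30 | 6 x 2 x 5 = 60 | 0 | 60 |
| 30 to 34 | 29 | 6 x 2 x 5 = 60 | 0 | 60 |
| 30 to 35 inclusive | 30 | 6 x 2 x 6 = 72 | 6 x 2 x 1 = 12 | 72 - 12 = 60 |
| 30 to 34 | 30 | 6 x 2 x 5 = 60 | 6 x 2 x 1 = 12 | 60 - 12 = 48 |

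The range is therefore 48 to 60, with 60 on the plain reading.

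**Step 2: control pairs as written.** Baseline gives 6 x 2 = 12. If a reading coincides at minute 30, the total is 12 + 12 = 24.

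**Step 3: control pairs if transcription continues.** With five infrared readings per foot, 12 + 60 = 72, still from only 6 women.

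**Step 4: scale against the spinal cohort.** Pre-spinal pairs are 60 x 2 = 120. If the 6 controls are counted within the 60, they are (60 - 6) x 2 = 54 x 2 = 108. The per-minute series between spinal injection and draping, and the readings after drape removal, add further pairs. The protocol does not give the length of those periods, so they are not counted here.

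**Step 5: the two schedules side by side.**

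| | Probe transcription ends | Infrared readings after draping | Same-minute probe value scheduled? |
|---|---|---|---|
| Spinal cohort | at transfer onto the bed | after drape removal, before transfer | yes |
| Controls | after 30 minutes | after 30 minutes, for 5 minutes | no (at most the first reading per foot) |

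**The case against.** The strongest reply is that the protocol never gives the controls a device-comparison role. They lie draped in theatre without a spinal while room and under-drape temperatures are recorded. That fits a check on whether draping and surroundings alone warm the feet, which bears on the primary question. For that purpose each device can be compared with its own baseline, and no simultaneous pairing is needed. This stands, and it is a main reason for the low grade.

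Second, the secondary question is already served by the spinal cohort, whose theatre infrared readings all fall inside the probe window. This also stands. Nothing in the protocol says that agreement between devices must be shown specifically after draping and without a block.

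Third, monitoring is described as continuous and removal of the probe is not mentioned, so values may still be visible on the monitor. That is true, but the plan does not ask anyone to write them down. A team that follows the text would have no record of them.

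Two stronger readings are tempting. A reader might infer a device bias of some size in degrees, from temperature drift between the last probe value and the infrared readings. The documents give no drift rate, and the protocol does not plan to subtract the minute-30 probe value from later infrared values, so no such figure can be supported. A reader might also infer that the infrared measurement site is left open because an adhesive probe occupies the skin. The Methods give one landmark, the dorsum above the space between the second and third metatarsals, and name both devices directly after it. The exact offset from the probe is bedside detail, and fixing it would not separate a constant site difference from device bias.

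**Conclusion.** The point holds as a minor one. As scheduled, 48 to 60 control infrared readings have no same-minute probe reading, although the protocol arranges such pairing for the spinal cohort. The count rests on one infrared reading per foot per minute, and its lower end on a probe reading coinciding with the first infrared reading at minute 30.

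The consequence is limited to the secondary device comparison: the plan supplies no simultaneous pairs after draping in women without a spinal, or 12 at most. It would be wrong to infer that the device comparison fails, that block-free pairs are absent, or that the probes are taken off at 30 minutes. The 12 control baseline pairs and the 108 to 120 pre-spinal pairs are all block-free, and the text is silent on probe removal. The primary question is not affected.

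**What to change.** In the control-group paragraph of the Methods, extend the one-minute probe transcription so that it runs through the 5-minute infrared series, with the two devices read in the same minute on each foot. This also removes the ambiguity at minute 30.

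The cost is a change of wording and 6 x 5 = 30 more minutes of probe transcription over the whole control group, with equipment already in use. The same double recording, both devices every minute, is already scheduled in the spinal cohort before draping, so it asks for no new procedure. The gain is up to 60 further control pairs, from 12 to 72 on the plain reading. They are repeated readings on 12 feet of 6 women, and so carry much less information than 60 independent pairs.
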